NorthShore’s well-established PDP includes universal perinatal outpatient depression screening with both centralized scoring and a referral network of community mental health providers, a 24/7 crisis hotline to respond to urgent/emergent patient needs, and relevant curriculum for obstetricians and nurse midwives.

MomMoodBooster + Perinatal Depression Program (MMB2+PDP)

Women in the MMB2+PDP group could use MMB2 and the PDP. MMB2 recommends increasing pleasant activities to regain life balance, interrupting negative thoughts and increasing positive thoughts, seeking support from others, and tracking mood. MMB2 included videos, audios, animations, and editable lists in a browser-based Web app that responsively adapted to each user’s device (smartphone, tablet, laptop, and desktop). During the 12-week active treatment phase, each of the six MMB2 sessions becomes available sequentially according to a weekly schedule. Thereafter, users could continue visiting MMB2 for 7 additional months. The study coordinator enrolled women to MMB2 using the program’s administrative website. Each pregnant woman’s due date was used by MMB2 to ask the participant if they had delivered their baby in order to change from pregnant to postpartum program content. Two team outreach calls were made by a NorthShore team member not trained in mental health treatment. Call #1, 2-4 weeks following randomization, focused on resolving any difficulties signing into MMB2. Call #2, scheduled after the posttest, collected open-ended feedback about the program.

Measures and Assessments

Participant characteristics were assessed at baseline and outcomes were assessed at baseline and the 12-week posttest. Participants who completed all assessments received a \$100 e-gift card.

In terms of primary outcomes, the Patient Health Questionnaire (PHQ-9) used to assess the severity of depressive symptoms has been well-validated, found reliable and sensitive, and widely used with perinatal depressed women – including in our prior MMB research, and other studies in large healthcare systems. We used the Depression Anxiety Stress Scale (DASS-21) Anxiety scale to assess anxiety symptom severity because perinatal anxiety is commonly comorbid with depression and has been related to adverse perinatal outcomes.

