For secondary outcomes, the DASS-21 stress scale was used to assess stress severity, the Behavioral Activation for Depression Scale (BADS-Short Form) to measure behavioral activation, the short-form version of the Automatic Thoughts Questionnaire (ATQ-SF) to measure negative thoughts associated with depression, and a measure of behavioral self-efficacy to assess use of MMB2 strategies to manage activities, positive/negative thinking, support, relaxation, and goal setting.

Additional measures included MMB2's continuous and unobtrusive tracking of each user's MMB2 visits, session visits (date, number, duration), and activities (e.g., number/duration of videos and animations viewed, personal list updates). In addition, women who visited MMB2 (confirmed by unobtrusive engagement metrics) were asked on the posttest to rate MMB2's usability and helpfulness, the helpfulness of team outreach calls, and whether they would recommend MMB2. Participants in both groups were asked whether they used other mood management products or programs while in the study.

STATISTICAL ANALYSIS PLAN

Preliminary analyses examined distributional properties of measures, baseline equivalency, and missing data. Intent-to-treat analyses of group effects were performed using fixed effects growth models fit (SAS PROC MIXED; Version 9.4) and estimated with maximum likelihood. Individual variability in outcomes from baseline to posttest were predicted by a two-level dummy coded group variable (coded 0 for PDP and 1 for MMB2+PDP), a time variable (coded in months elapsed between baseline and posttest), and a group \times time interaction. Effect sizes for the group \times time interaction are equivalent to Cohen's d. Moderation of group \times time effects for the primary depression outcome (PHQ-9) were evaluated by adding in separate models, the main effects of baseline perinatal status (pregnant/postpartum), the EPDS primary screen, baseline PHQ-9, and all two- and three-way higher order interactions with group and time.

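### The baseline PHQ-9 moderation model uses the same score as time-0 outcome and as predictor, so its three-way test is over-precise when posttests are missing, or cannot be fitted properly

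*Combined protocol and SAP*

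**What the plan says.** Under Measures and Assessments, "outcomes were assessed at baseline and the 12-week posttest", and PHQ-9 is a primary outcome. PHQ-9 is therefore measured twice per woman.

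The Statistical Analysis Plan states: "Intent-to-treat analyses of group effects were performed using fixed effects growth models fit (SAS PROC MIXED; Version 9.4) and estimated with maximum likelihood". It continues: "Individual variability in outcomes from baseline to posttest were predicted by a two-level dummy coded group variable", together with elapsed months and a group × time term. The baseline score is thus a row of the response, at time 0.

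For moderation, "effects for the primary depression outcome (PHQ-9) were evaluated by adding in separate models", the additions being the main effects of baseline perinatal status and of "the EPDS primary screen, baseline PHQ-9, and all two- and three-way higher order interactions with group and time".

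The plan names no RANDOM or REPEATED structure and no robust standard error. It gives no sample size, significance level or expected share of missing posttests. It does not say that the baseline row is dropped from the response when baseline PHQ-9 becomes a predictor.

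**The concern.** In the third moderator model the time-0 rows have baseline PHQ-9 on both sides of the equation. They fit perfectly or almost so, and carry no information about residual variation. A model with one variance for both visits does not know this. It averages the empty baseline residuals with the real posttest residuals, and it treats a woman with only a baseline row as informative about the three-way term.

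That term is the planned test of whether the benefit of MMB2 depends on initial depression severity. If its standard error is too small, severity could too easily be reported as modifying the effect, with a confidence interval that is too narrow, and the error grows with dropout. Perinatal status and the EPDS screen are not the time-0 response, so those models do not have the problem.

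**Working it through.** The plan gives no figure to reproduce, so the check is algebra followed by simulation.

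**Inputs.** From the documents: two PHQ-9 measurements, the baseline score in the response, maximum likelihood, and an intent-to-treat analysis that keeps baseline-only women in the fit. Assumed: two-sided 5% level, 0–40% missing posttests and, unless stated, N = 200 and posttests missing independently of PHQ-9.

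**Notation.** N women have a baseline and n₁ a posttest; p = n₁/N. σ² is the posttest residual variance given group and baseline. In a regression on n women at one visit, the group × baseline coefficient has variance cσ²/n, where c depends on allocation and on the spread of baseline scores.

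**1. Common variance, equal elapsed times.**
- Time-0 fit: slope 1 on baseline PHQ-9, all other time-0 coefficients 0, all N residuals 0.
- Pooled variance: n₁σ²/(N + n₁).
- Model variance of the three-way effect at posttest: n₁σ²/(N + n₁) × c(1/N + 1/n₁) = cσ²/N.
- True variance: cσ²/n₁, because the time-0 fit has no sampling error.
- Ratio of reported to true SE: √(n₁/N) = √p. Means and SDs do not enter.

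Example with N = 200 and n₁ = 160: the pooled variance is (160/360)σ² = 0.444σ². Multiplied by (1/200 + 1/160) = 0.01125 this gives 0.0050σ², against a true 0.00625σ². The SE ratio is √0.8 = 0.894. The effective critical value is 1.96 × 0.894 = 1.753, so the type I error is 8.0%.

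With n₁ = N, the halved variance is offset by a baseline error that the model charges but that does not exist. The ratio is 1.

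If dropout depends on baseline PHQ-9, the squared ratio is at most 2p/(1 + p), still below 1 whenever p < 1.

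**2. Random intercept.** With equal elapsed times, the profile −2 log-likelihood in the within-woman correlation ρ is −N log(1 − ρ²) plus a constant. It is smallest at ρ = 0, so the intercept variance is estimated as 0 and case 1 returns. In the random-intercept simulations, including those with varying elapsed times, it was estimated at 0 in every fit.

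**3. Visit-specific or unstructured covariance.** The four time-0 coefficients can reproduce baseline PHQ-9 exactly, whatever the elapsed times. The likelihood is unbounded as the time-0 variance goes to 0.

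**4. Simulation under no three-way effect.** Ranges cover several independent sets of runs at N = 200 (2,000–4,000 per setting), with common variance or random intercept and with equal or varying elapsed times.

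| Missing posttests | √p | Type I error, formula | Type I error, simulated |
|---|---|---|---|
| 0% | 1.000 | 5.0% | 4.8–6.6% |
| 10% | 0.949 | 6.3% | 6.2–7.7% |
| 20% | 0.894 | 8.0% | 8.1–10.2% |
| 30% | 0.837 | 10.1% | 10.5–12.9% |
| 40% | 0.775 | 12.9% | 13.9% (one set) |

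At 5% missing the formula gives only 5.6%. Regressions using posttest rows only, fitted to the simulated data, gave 4.2–5.8%.

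Further settings:
- N = 100 to 400, common variance: 5.9–8.8%, 8.4–9.8% and 10.5–12.4% at 10%, 20% and 30% missing.
- N = 1000, 20% missing: 7.8%, SE ratio 0.893.
- Dropout depending on baseline PHQ-9: 6.9–7.8%, 9.2–9.7% and 11.9–12.1%, against 4.4–5.3% for posttest-only regression.
- Elapsed-time SD 0.5 months: baseline residuals are no longer exactly zero but have a root mean square of only 0.13–0.17 points. Growth-model and ANCOVA estimates then differ by 0.04–0.05 on average, against a sampling SD of 0.13–0.15.

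**The case against.** The strongest reply concerns weight, not mechanism. Everything that sets the size is assumed: the documents give no dropout rate, sample size, significance level or covariance structure. There is one follow-up at 12 weeks and a gift card for completing all assessments, and nothing shows that 20–30% of posttests were lost. A visit-specific structure would probably announce itself with a convergence or variance warning. A cluster-robust standard error, which the plan does not exclude, would bring the type I error to 5.7–7.0%. The plan attaches no decision rule to moderation, and this is one of three moderators for one outcome.

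Much of this stands as a limit on the consequence. With little dropout the practical harm is small. The √p rule is exact only for equal elapsed times and missingness unrelated to baseline. Not all the simulated excess comes from dropout: with complete posttests and elapsed-time SD 0.5 months, one set of runs gave 6.4%, 6.1% and 5.9% at N = 100, 200 and 400, which reflects maximum-likelihood variance estimation and varying times.

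The objection does not rescue the model. Each covariance structure considered gives either too small a standard error under dropout or a degenerate fit. The plan names no robust standard error, and even that did not fully restore the level.

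**Conclusion.** The concern holds. As written, the baseline PHQ-9 moderation model regresses the time-0 outcome on itself, and nothing elsewhere in the documents prevents it. Under a common variance or random intercept, the three-way standard error is about 5%, 11% and 16% too small at 10%, 20% and 30% missing posttests (1 − √p), somewhat more in most simulations. A nominal 95% interval then covers about 93.7%, 92.0% and 89.9% by formula. Under visit-specific variances the fit is degenerate.

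The direction and the √p result follow from the model. The realised size depends on the unstated dropout rate and covariance structure. The scope is one planned moderation test on a primary outcome, so this should be corrected but does not touch the main trial result.

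**What to change.** For the baseline PHQ-9 moderator only, replace the growth model by a linear regression of posttest PHQ-9 on group, centred baseline PHQ-9 and group × baseline PHQ-9, among women with a posttest. Read moderation from the product term. Adjustment for perinatal status, the blocking factor in the randomization, is optional and not needed for the repair. Keep the growth model for the main group × time tests and for the perinatal-status and EPDS moderators.

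The cost is one sentence in the SAP and one regression, with no new data. The SAP is written in the past tense, so if the growth-model version has been run, this analysis should be re-run and the new result reported. The effect is then expressed at posttest rather than per month. Women without a posttest drop out of this test; with equal elapsed times the point estimate is identical, so all that is lost is precision that was not real.
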